To minimise the variability of the response to AZD9668 that could occur as a result of patients being on different background medications for COPD, all patients will be standardised to maintenance therapy with tiotropium. This will entail patients on inhaled GCS (including combination therapy with LABA) being withdrawn from that treatment, and switched to tiotropium only. However, this would only be done with the patient's express consent and if the investigator assesses that it is safe to do so. To mitigate the risks associated with inhaled GCS withdrawal, only patients with an FEV1 of  $\geq$ 40 % of predicted normal value will be recruited to this study. Also, as all patients will receive tiotropium, the risk of inhaled GCS withdrawal in a short-term study is considered to be small. Additionally, patients will be closely monitored during the run-in period and throughout the study with daily FEV1 and PEF measurements and symptom diaries. The use of MSCT involves ionizing radiation that increases the risk of radiogenic tumors in patients. The data related to biological effects of CT radiation and recommendations from different committees has been considered in the design of the study (Mayo JR 2008). The risk is known to be age and gender dependant and higher in children, young adults, women, and pregnancy (high radiosensitive group). The risk from radiation exposure is known to be cumulative, and may involve other factors like use of contrast agents. MSCT has been applied in several clinical studies for COPD and asthma and the risk-benefit evaluation has been done, and literature is available. AstraZeneca has considerable experience in appplicaton of CT imaging for COPD and has been involved in population studies and cross sectional studies (Brown RH et al 2005, Coxson HO et al 2008b, Capraz F et al 2007, Lee YM et al 2004). The understanding of the risk – benefit aspects helps in optimising the CT radiation dose to the endpoint. Since the participation in the present study may not offer direct benefit to the patient, a dose constraint will be applied based on ALARA (As Low As Reasonably Achievable) principle. Detailed information on the potential risks of radiation, the aims, methods, benefits and potential hazards of the study will be given to patient during the informed consent process.

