# 3.1 Overall study design and flow chart

This is a 12-week randomised, double-blind, placebo-controlled, parallel-group, multi-centre phase IIb study to assess the effect of AZD9668 on structural changes in the airways in COPD patients. The primary variable is AWT-Pi10 assessed by MSCT.

The plan is to enrol approximately 70 patients, men and women aged 50 to 80 years inclusive, to obtain approximately 50 randomised patients. Approximately 15 centres in Canada and Europe are planned to participate in the study with 3 to 10 patients per centre.

There will be 8 visits to the clinic: Visit 1a (enrolment), Visit 1b (screening), Visit 2 (randomisation), Visits 3, 4, 5 and 6 (after 1, 4, 8 and 12 weeks of treatment) and Visit 7 (follow-up).

All inclusion/exclusion criteria that can be assessed at each visit should be checked carefully, including patients suitability to use electronic devices/perform home spirometry, before therapy is changed and before randomisation.

At Visit 1a all patients will be informed about the study and, if willing to take part in the study, sign the informed consent form and have demographic data collected. Signing the informed consent form must be done before any study-related procedures, restrictions or screening assessments are performed. The timing of this visit in relation to Visit 1b will be dependent on the medication being taken by the patient on entry to the study as described in Section 5.5.3.2.

At Visit 1b, all patients must be on tiotropium alone as maintenance therapy. In addition to tiotropium maintenance therapy, patients will be allowed to use short-acting  $\beta_2$ -agonists (SABA) as reliever medication throughout the study. See Section 5.5.3.2 regarding provision of tiotropium and SABA.

At Visit 1b, patients will be screened and evaluated for eligibility to enter the 14-17 day run-in period. Included patients must have a documented COPD history with symptoms for at least 1 year according to GOLD 2008, and they must be ex-smokers with a smoking history of at least 10 pack years. Their FEV1 must be 40 - 70% of the predicted normal value and FEV1/FVC <70%, both values post-bronchodilator.

Included patients will be asked to fill in an electronic diary and to measure  $FEV_1$  and PEF morning and evening from Visits 1b to 6.

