#### **3.2.1** Rationale for patient population and control groups

The patients with a  $FEV_1$  range of 40 - 70% predicted are selected for this study with the expectation that at these levels of  $FEV_1$  they will have sufficient airways disease detectable by CT and that be able to show a response to treatment, while avoiding patients with too severe disease who may deteriorate on withdrawal of ICS/LABA. To reduce the radiation risk only patients aged 50 years or above will be enrolled as older patients have a reduced risk of cancer from ionising radiation.

To minimise the variability that could occur as a result of patients being on different medications for COPD, all patients will be standardised to maintenance therapy with tiotropium.

To provide a comparator for the treatment effects of AZD9668 a placebo group is chosen as a standard design for estimating efficacy.

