# 4.1 Inclusion criteria

For inclusion in the study patients should fulfil the following criteria:

- 1. Provision of informed consent prior to any study specific procedures at Visit 1a.
- 2. Male or female aged 50-80 years inclusive at Visit 1b. Female patients may be of non-childbearing potential (ie, post menopausal or surgically sterile) or of child bearing potential:
  - Women will be considered post menopausal if they are
     i) over 50 years old and have been amenorrheic for 12 months or more following cessation of all exogenous hormonal treatments or
     ii) over 57 years old

- Surgically sterile is defined as having undergone hysterectomy and/or bilateral oophrectomy and/or bilateral salpingectomy; tubal ligation on its own is not adequate
- Women will be considered of child bearing potential if they are between menarche and menopause, and have not been permanently or surgically sterilised. Women of child bearing potential must have a pregnancy test at Visit 1b and at Visit 2 prior to randomisation, and at the follow up visit, and must be using suitable methods of birth control. Further details of methods of birth control that are considered suitable for use are given in Section 5.1.
- 3. Documented clinical diagnosis of COPD, according to GOLD guidelines (GOLD 2008) with symptoms for  $\geq 1$  year before Visit 1b.
- 4. Ex-smokers for at least 12 months prior to Visit 1b.
- 5. A smoking history of at least 10 pack years (1 pack year = tobacco consumption corresponding to 20 cigarettes smoked per day for 1 year).
- 6. FEV1 40-70% (inclusive) of the predicted normal value (post-bronchodilator) at Visit 1b.
- 7.  $FEV_1/FVC < 70\%$  (post-bronchodilator) at Visit 1b.
- 8. Able to use the handheld electronic devices (assessed at Visit 1a).

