### 4.3 Exclusion criteria

Patients should not enter the study if any of the following exclusion criteria are fulfilled:

- 1. Any clinically relevant disease or disorder (eg, infectious/viral disease (including hepatitis B or C) cardiovascular, pulmonary other than COPD, gastrointestinal, liver, renal, neurological, musculoskeletal, endocrine, metabolic, malignant, psychiatric, major physical impairment), past or present, which in the opinion of the Investigator, may either put the patient at risk because of participation in the study, or may influence the results of the study, or the patient's ability to participate in the study.
- 2. Significant or unstable ischemic heart disease, arrhythmia, cardiomyopathy, heart failure, uncontrolled hypertension, or any other relevant cardiovascular disorder as judged by the Investigator.
- 3. Current diagnosis of asthma according to GINA guidelines (GINA 2008).
- 4. Malignancy or neoplastic disease within the past 5 years other than treated basal/squamous cell skin carcinoma or treated cervical cancer in situ.
- 5. Patients who require long term oxygen therapy (LTOT).
- 6. Worsening of COPD within 4 weeks prior to Visit 1b and during the run-in period (defined as an increase in respiratory symptoms requiring hospitalisation and/or a course of oral glucocorticosteroids and/or increased usage/dose of inhaled steroids and/or antibiotic treatment).
- 7. Acute infections requiring treatment in the 4 weeks prior to Visit 1b and during the run-in period.
- 8. Any clinically relevant abnormal findings in physical examination, vital signs, haematology, clinical chemistry, or urinalysis at Visit 1b, which in the opinion of the Investigator, may put the patient at risk because of his/her participation in the study, or may influence the results of the study, or the patient's ability to participate in the study.
- 9. A QTcB interval of >450 msec for males and >470 msec for females at Visit 1b.
- 10. Any ECG abnormality (including arrhythmia), which in the opinion of the investigator may put the patient at risk or interfere with study assessments at Visit 1b.

- 11. A past history of or current clinical or laboratory evidence of renal failure, or an estimated creatinine clearance of <50 mL/min (as calculated by the Cockcroft-Gault formula) at Visit 1b.
- 12. Alanine aminotransferase (ALT) and/or aspartate aminotransferase (AST) level  $\geq 1.5$  x upper limit of normal (ULN) at Visit 1b.

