# 5.2 Patient enrolment and randomisation

The Principal Investigator will:

- 1. Obtain signed informed consent from the patient before any study specific procedures are performed.
- 2. Assign the patient a unique enrolment number, beginning with "E0001001 (EXXXXYYY)" where XXXX reflects the centre number and YYY will be allocated sequentially to enrolled patients at each centre
- 3. Determine patient eligibility. See Sections 4.1, 4.2 and 4.3.
- 4. Assign eligible patient unique randomisation code (patient number) at Visit 2.

Re-enrolment is allowed only if enrolment has failed due to technical problems, eg, with the eDiary. Patients failing to meet an inclusion or meeting an exclusion criterion must not re-enter the study. If a patient discontinue the study after randomisation he/she can not re-enter the study.

If a patient withdraws from participation in the study, then his/her enrolment/randomisation code cannot be reused. Patients who discontinue the study after randomisation will not be replaced.

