## 5.5.3.2 Open treatment during enrolment, run-in and treatment periods

Patients who use inhaled glucocorticosteroids (GCS) (including combination therapy with long-acting  $\beta_2$ -agonists (LABA) before the study should, based on the investigator's judgement that it is safe for the patient and after signing informed consent, stop inhaled GCS (including combination products) at Visit 1a, >3 weeks before attending the screening visit (Visit 1b), i.e., these patients will be on tiotropium for at least 5 weeks before randomisation. These patients will receive tiotropium at the same occasion (Visit 1a).

Patients not taking inhaled GCS prior to the study will begin treatment with tiotropium at Visit 1b. For these patients, Visit 1a can be performed closer to Visit 1b. The informed consent must be signed prior to any medications being withheld and timeframes for withholding medications taken into account (see Section 5.6.3). At Visit 1b, all patients must be on tiotropium alone as maintenance therapy.

Eligible patients will be enrolled to a 2 week run-in period, during which all patients will be treated with tiotropium 18 µg once daily.

The patients will be provided with maintenance and reliever medication throughout the run-in period and treatment period. Spiriva® (tiotropium bromide, 18 µg/dose, 30 capsules/package) will be provided by AstraZeneca R&D or be supplied locally by the AstraZeneca Marketing Company (MC). The reliever medication, VentolinTM EvohalerTM (salbutamol sulphate 100 µg/dose, 200 actuations), will be supplied locally by the AstraZeneca MC or prescribed by the investigator. Products provided must contain the same active ingredient and use the same dosage form and be an equivalent strength as the medications specified in Section 5.5.2. When tiotropium and salbutamol are locally sourced local regulatory guidelines will be adhered to.

If the patient prefers to use their existing reliever medication (SABA only, dry powder inhalers are allowed) they may do so. If so, the same SABA should be used throughout the study.

When receiving the reliever and maintenance medications, the patient will be carefully instructed and trained on how to inhale from the inhalers to ensure good inhalation technique during the study. Written information will be provided to each patient in his/her local language.

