## 6.3.4 Lung function measurements by spirometry

Pulmonary function,  $FEV_1$  (L), FVC (L) and SVC (L), will be measured by spirometry (preand post-bronchdilator) and collected in the eCRF at Visits 1b to 6 as defined in Table 2. Measurements at Visits 2 to 6 should be performed pre-dose of AZD9668.

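### The FEV1 floor offered as a safeguard for inhaled steroid withdrawal is not required to be checked until Visit 1b, more than 3 weeks after the steroids stop at Visit 1a

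*Protocol*

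**What the plan says.** Two rationale sections tie the FEV1 limits to steroid withdrawal. Section 1.4 states: "To mitigate the risks associated with inhaled GCS withdrawal, only patients with an" FEV1 at or above 40% of predicted will be recruited. Section 3.2.1 says the 40-70% range should leave enough detectable airway disease "while avoiding patients with too severe disease who may deteriorate on withdrawal of ICS/LABA".

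The schedule runs as follows for patients on inhaled glucocorticosteroids (GCS) at entry:

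- **Withdrawal.** Section 5.5.3.2 has them "stop inhaled GCS (including combination products) at Visit 1a, >3 weeks before attending the screening visit (Visit 1b"), subject to signed consent and the investigator's judgement that stopping is safe. They receive tiotropium on the same occasion.
- **FEV1 criterion.** Inclusion criterion 6 (Section 4.1) requires FEV1 "40-70% (inclusive) of the predicted normal value (post-bronchodilator) at Visit 1b".
- **Spirometry.** Section 6.3.4 has it "collected in the eCRF at Visits 1b to 6 as defined in Table 2", and Table 2 marks none at Visit 1a. Percent predicted for eligibility is calculated from the Visit 1b value.
- **Eligibility checks.** Table 2 schedules one at Visit 1a. Section 3.1 says "All inclusion/exclusion criteria that can be assessed at each visit should be checked carefully" before therapy is changed.
- **Pre-screening.** Section 6.2 lists age, COPD history and medication, smoking history, concomitant medication and medical history. It does not name FEV1.
- **Home monitoring.** Sections 6.3.5 and 6.3.8 dispense the device at Visit 1b, with recordings from that evening.

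**The concern.** A floor meant to limit the risk of stopping a treatment needs to act before the treatment is stopped. Here the rationale and the schedule are out of step: the floor governs who continues after Visit 1b, and nothing requires it to govern whose steroids are stopped at Visit 1a.

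At stake is the safety of the patients Section 3.2.1 means to avoid. A patient below 40% of predicted can be withdrawn, found ineligible more than 3 weeks later, and then be barred from another attempt, since Section 5.2 says: "Patients failing to meet an inclusion or meeting an exclusion criterion must not re-enter the study". That patient has had the withdrawal without taking part in the trial.

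The protocol does put a check before an exposure elsewhere. Sections 1.4 and 3.1 require the Visit 1b laboratory results to be reviewed before the baseline CT, so that no one is irradiated needlessly. Steroid withdrawal has no comparable FEV1 check in front of it.

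**Working it through.** **1. Reproduce the protocol's own timing.** Section 5.5.3.2 says prior inhaled GCS users are on tiotropium for at least 5 weeks before randomisation.
- Visit 1a to 1b: more than 3 weeks, so more than 21 days (Table 1, Section 5.5.3.2).
- Visit 1b to 2: 14-17 days (Table 1).
- Sum at the lower end: more than 21 + 14 = more than 35 days, which is 5 weeks. The stated figure is reproduced.

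**2. Time from withdrawal to the first required FEV1 check.** More than 21 days, so at least 22 whole days. The synopsis, with an enrolment period of up to 21 days, would give 21.

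**3. Is the check required earlier by another route?**
- The Section 3.1 instruction and the Visit 1a eligibility check reach only criteria that can be assessed at that visit. Criterion 6 is assigned to Visit 1b, whereas criterion 8 (use of the handheld devices) is expressly assigned to Visit 1a.
- The investigator's safety judgement is mandatory but needs no FEV1 value. Consulting one on file is permitted, not required.
- The optional practice session at Visit 1a in Section 6.3.4 concerns the slow manoeuvre and lies outside the assessment schedule.

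None of these makes the floor binding at Visit 1a.

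**4. What covers the interval?**
- At withdrawal: express consent, investigator judgement, exclusion 5 (long-term oxygen) and tiotropium.
- Exclusion 6, "Worsening of COPD within 4 weeks prior to Visit 1b and during the run-in period", looks back 28 days. It spans the 22-day minimum with 28 - 22 = 6 days to spare, but it acts only after a worsening.
- Adverse events are collected from consent and followed up as medically needed, but the first questioning is at Visit 1b (Section 6.4.3).
- The daily FEV1, PEF and diary monitoring cited in Section 1.4 starts with the run-in, so it does not cover these weeks.

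**5. How much time off steroids precedes the check?** Visit 2 to Visit 6 is 12 weeks less up to 3 days, or 81-84 days (Table 1). At the minimum 22-day interval:
- Full participation, shortest: 22 + 14 + 81 = 117 days.
- Full participation, longest: 22 + 17 + 84 = 123 days.
- Share elapsed by Visit 1b: 22/123 = 17.9% to 22/117 = 18.8%.

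The Visit 1b test therefore spares a failing patient the remaining 95/117 = 81.2% to 101/123 = 82.1% of study-required days off inhaled steroids.

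**6. Number of patients affected.** This cannot be derived. The protocol gives no proportion using inhaled GCS at entry, none below 40% of predicted, and none with an FEV1 on file.

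**The case against.** The best defence is that the protocol speaks of patients recruited to and selected for the study, and the Visit 1b test delivers that floor before run-in, CT and 12 weeks of treatment. The formal test belongs after washout because patients must by then be on tiotropium alone. At withdrawal, the investigator must judge that stopping is safe, the patient must consent, and tiotropium starts the same day. Section 1.4 considers the remaining risk small in a short-term study. Being withdrawn and then failing screening is common to any washout-then-screen design: about 70 are to be enrolled for 50 randomised, and an early FEV1 check removes only one reason for failure.

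Most of this stands, and it limits the size of the point. It does not remove it. Section 1.4 lists the floor alongside investigator judgement as a separate mitigation, and the floor does not operate when withdrawal begins.

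Three stronger readings are tempting but unsupported:

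- **That patients below 40% may enter the randomised comparison or distort the primary analysis.** The Visit 1b test stands between them and randomisation.
- **That withdrawal is unprotected.** The safeguards in step 4 of the working are real, though none requires an FEV1 value.
- **That 18-19% measures the risk incurred.** It is a share of calendar days. The protocol gives no deterioration risk by week or by FEV1 level.

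**Conclusion.** The point holds as a modest patient-safety improvement. Sections 1.4 and 3.2.1 offer FEV1 of at least 40% of predicted as protection against the risk of inhaled steroid withdrawal, but the protocol requires no FEV1 check until at least 22 days after withdrawal, and daily monitoring is absent over the same weeks. A fully compliant site can withdraw steroids from a patient below the floor.

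The conclusion rests on the visit schedule alone and applies only to patients using inhaled GCS at entry, with or without a long-acting beta-agonist. It assumes no site practice beyond what is written; a site that routinely consults recent spirometry would already have narrowed the gap. The randomised population, the primary analysis, the sample size and the power are all untouched.

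**What to change.** Amend Section 5.5.3.2 and Table 2, with a cross-reference in Sections 5.1 and 6.3.4, along these lines:

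> For patients on inhaled GCS, a documented post-bronchodilator FEV1 of at least 40% of predicted normal (sponsor's reference list), obtained within a look-back window fixed by the sponsor, must be on file before inhaled GCS are stopped at Visit 1a. If none is on file, or the value on file is below 40% or pre-bronchodilator, a post-bronchodilator FEV1 may be measured at Visit 1a after consent, and inhaled GCS are stopped only if it is at least 40%. The medication restrictions of Section 5.6.3.1 do not apply to this safety check.

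The sponsor must set the window; 12 months is an illustrative assumption. The waiver has to cover the whole of Section 5.6.3.1, because Sections 5.1 and 6.3.4 apply that full list before clinic lung function tests and it includes inhaled GCS, anticholinergics and xanthines. Apply no 70% ceiling here, so that a patient above 70% on current treatment who falls into range on tiotropium is not lost. Keep the Visit 1b test as the formal 40-70% eligibility test.

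**Cost.** A records check for inhaled GCS users; the reference list already exists. Patients without a usable value need a short session: 15 minutes' rest plus a 15-30 minute wait after salbutamol, so 15 + 15 = 30 to 15 + 30 = 45 minutes plus manoeuvres, and a height if none is recorded. A few patients would be turned away earlier, including some who might have reached 40% at Visit 1b. A value taken on combination treatment can still pass a patient who later fails at Visit 1b, so the gap narrows without fully closing.

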# 2. STUDY OBJECTIVES

# 2.1 **Primary objective**

The primary objective of the study is to evaluate structural changes effected by AZD9668 in the airways of adults with COPD by MSCT.

Primary outcome variable aligned to the primary objective:

- AWT-Pi10 (airway wall thickness of a theoretical airway with an internal perimeter of 10 mm) (See Section 3.2.3)

Secondary outcome variables aligned to the primary objective:

- 5th generation wall area % (See Section 3.2.3)
- Air Trapping Index (ATI) on expiratory scans (See Section 3.2.3)

Exploratory outcome variables aligned to the primary objective:

- Volume adjusted 15th percentile density (See Section 3.2.3)
- Mean wall area % for airways of 4th to 6th generation (See Section 3.2.3)
- Emphysema index (or relative area) (See Section 3.2.3)

# 2.2 Secondary objective(s)

The secondary objectives of the study are:

- To relate structural changes in the airways to pulmonary function variables and symptoms of COPD
- To evaluate safety of AZD9668 in COPD patients

Outcome variables aligned to these objectives are: *Lung function parameters* 

- pre-bronchodilator IC, TLC, FRC, RV and SGaw
- pre-bronchodilator DLCO
- pre- and post-bronchodilator FEV1, FVC and SVC
- PEF morning and evening (daily recordings)
- FEV1 morning and evening (daily recordings)

